a) SMI patients with antipsychotic associated obesity who participate in a behavioral intervention that includes classes on Lifestyle Balance will gain more knowledge (i.e., greater change scores on before/after survey test instrument) about general health issues (e.g., nutrition, importance of exercise.) than a control group receiving “usual psychiatric care”.

b) SMI patients with antipsychotic associated obesity who participate in a behavioral intervention program will achieve better cardiovascular (e.g., sustained weight loss, better glucose tolerance, improved lipid profiles, and improvement in other biological measures, e.g. insulin and c-reactive protein) and mental health (e.g., improvements in general measures of psychopathology, subjective quality of life, etc) outcomes than the control group. A larger proportion of patients who take the Lifestyle Balance classes will actually make lifestyle

changes (objectively measured by food and exercise diaries) than patients in the usual care group given ordinary counseling.

c) A larger proportion of patients who take the Lifestyle Balance classes will actually make lifestyle changes (objectively measured by food and exercise diaries and exit interviews) than patients in the usual care group given ordinary counseling. Analysis plan: For all hypotheses concerning the effects of the treatment program use analysis of repeated measures using the assessments at baseline, 8 weeks, 6 months, and 12 months. These analyses will provide information about maintenance of treatment effects. We will use a mixed general linear model with timepoints nested within patients. For hypothesis (c) we will adapt the mixed general linear model to dichotomous data by using a logistic link function to model the likelihood of life style changes. We will include all patients with at least one post-baseline data point in the analysis to maximize power. We will also consider the appropriateness of linear growth curve mixed effects models, i.e., fitting an intercept and linear slope for each treatment group as fixed effects, and separate intercepts and linear slopes for each patient as random effects. Analyses of linear trends over time with a single df effect are often more powerful tests of differences in trends than multiple df profile contrasts across the separate time points.

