It provides valid statistics even in cases where there are more potential predictors than observations, and allows us to include all demographic, psychosocial, psychiatric and medical data known at baseline as potential predictors. The results of this analysis will suggest which patients are most likely to profit from further interventions, and it will also characterize the most at risk patients.

c) Subjects will continue to give meaningful, informed consent to participate throughout the study. They will see no significant decrease in their score on the informed consent quiz given every 6 months.

Analysis plan: A general linear model (GLM): ANOVA will be performed to compare the informed quizzes score results at 0, 6, and 12 months during the subjects' participation in the study.

5. Power Analysis: All calculations are based assuming a conventional medium effect size ($f=.25$, Cohen 1988); and a two-tailed alpha set at 0.05. Tuomilehto et al. estimated the SD of weight loss at roughly 5 kg across several treatment conditions (lifestyle changes vs. control) (76). A medium effect would thus translate into a group difference of about 2.5 kg or about 5.5 pounds. With an enrollment of $N=120$ and an estimated attrition rate of 45% we expect that at least 66 subjects will provide complete the study and provide 4 data points. The power analyses below are based on a sample size of $N=66$, i.e. this is a very conservative estimate due to the fact that the mixed linear model allows us to include cases with missing values in the analyses and that while they don't provide as much information as complete cases they still provide some information and will increase power. For the between-group comparisons, $N=66$ yields power=.7199 for main differences between groups if we assume that the within subject correlation is $r=.50$. Power to test for the difference in outcome trajectories of time – our main outcome variable is 0.99, and even if the effect is as small as $f=0.15$ we will have sufficient power to distinguish between the trajectories of the two treatment groups (power=0.83) insuring that we will get significant, insuring that we Preliminary data analyses shows that these assumptions are quite conservative and that effect sizes seem to be slightly larger than projected, suggesting that the final power will exceed the estimates presented here.

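### The .7199 main-effect power needs the 2.5 kg difference averaged over four visits, one of which is baseline; with 2.5 kg at the three later visits it is about 0.47 for 66 completers

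*Combined protocol and SAP*

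**What the plan says.** Section V.N.5 (Power Analysis) assumes a "conventional medium effect size ($f=.25$, Cohen 1988") and "a two-tailed alpha set at 0.05". It takes an outside study that "estimated the SD of weight loss at roughly 5 kg across several treatment conditions", and so reads the medium effect as a "group difference of about 2.5 kg or about 5.5 pounds". The sample size is built up as "With an enrollment of $N=120$ and an estimated attrition rate of 45" per cent, so that "at least 66 subjects will provide complete the study and provide 4 data points". On that basis N=66 "yields power=.7199 for main differences between groups if we assume that the within subject correlation is" .50. The section then gives 0.99 for the difference in trajectories, which it calls the main outcome, and 0.83 for that test at f=0.15.

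Section V.N, Statistical Plans (Primary Hypotheses), says which four data points these are: the treatment hypotheses "use analysis of repeated measures using the assessments at baseline, 8 weeks, 6 months, and 12 months". The same paragraph admits every patient with at least one post-baseline value.

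The Repeated measures analyses paragraph fits an intercept and slope through baseline, so baseline is part of the response. The covariates named for all analyses are the olanzapine and clozapine indicators, with propensity scores and site added if needed. The baseline value of the outcome is not named as a covariate, and baseline means are not constrained to be equal across arms.

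**The concern.** A group main effect over four visits compares each patient's average over all four. One of those visits precedes treatment, so its expected difference is zero and it dilutes the treatment effect. If 2.5 kg is the difference that treatment produces, the averaged difference is at most three quarters of it, 1.875 kg. A power figure that uses the full 2.5 kg for the average describes a larger effect than the one stated in kilograms.

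At stake is whether one of the two power claims in V.N.5 can be relied on. A reader would take from it that a main-effect test detects a 5.5 lb effect about 72% of the time. The trajectory claim in the same paragraph applies the same f=.25 to a different contrast, so it needs the same check.

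**Working it through.** **Inputs.** From V.N.5: two-sided alpha 0.05; f=.25, which for two equal groups is d=0.5 (2.5 kg / 5 kg); N=66; m=4 data points; r=.50. From Statistical Plans: visits at baseline, 8 weeks, 6 months (week 26) and 12 months (week 52). Assumed here: 1:1 allocation (33 per arm, ratio not stated) and equal correlation between all visits.

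**1. The plan's figure.** The noncentrality for a between-group factor is λ = f²·N·m / [1+(m−1)r] = 0.0625 × 66 × 4 / 2.5 = 6.6. With F(1, 64), power is 0.716 against the stated .7199. Three data points give 0.688. Five give 0.733, which is also close, but the plan says four. The interaction formula λ = f²·N·m/(1−r) with m=4 and F(3, 192) gives 0.999 at f=.25 (λ=33) and 0.828 at f=.15 (λ=11.88), against the stated 0.99 and 0.83. All three figures fit a four-visit calculation.

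**2. Same test, no difference at baseline.** The variance of a four-visit mean, in SD² units, is (1+3×0.5)/4 = 0.625. Then λ = (N/4) × (mean difference)² / 0.625, where N/4 = 16.5.

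| Difference at weeks 0, 8, 26, 52 (SD) | Four-visit mean | λ | Power |
|---|---|---|---|
| 0.5, 0.5, 0.5, 0.5 | 0.500 | 6.60 | 0.716 |
| 0, 0.5, 0.5, 0.5 (flat) | 0.375 | 3.71 | 0.475 |
| 0, 0.25, 0.5, 0.5 (half at week 8) | 0.3125 | 2.58 | 0.35 |
| 0, 0.077, 0.25, 0.5 (linear rise) | 0.207 | 1.13 | 0.18 |

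A simulation of 20,000 trials gave 0.475 for the flat case. With r=.30 or .70 the flat case gives 0.59 or 0.40.

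**3. Partial data (flat case, r=.50, data missing at random).** How many visits the 54 dropouts supply is an assumption. If 27 give baseline and week 8, power is 0.52 for a model with a single group effect and 0.59 for averaged group-by-visit means. If all 54 do, it is 0.57 and 0.68. If all 120 complete, it is 0.73. About 118 completers would be needed to reach 0.72.

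**4. The other reading of f.** For a four-visit mean difference of 0.5 SD with zero at baseline, the post-baseline difference must be 0.5 × 4/3 = 0.667 SD, or 3.3 kg. Power is then again 0.716.

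**5. Baseline-adjusted mean of the three later visits.** The residual variance is (1+2r)/3 − r² = 0.667 − 0.25 = 0.417. In the flat case λ = 16.5 × 0.25 / 0.417 = 9.9, and F(1, 63) gives 0.87 (simulation 0.86). Half at week 8: mean 0.417, λ=6.88, power 0.73. Linear rise: mean 0.276, λ=3.01, power 0.40. All use 66 completers.

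**6. Trajectory test on the same basis.** Half-differences around the visit mean in the flat case are −0.1875 once and +0.0625 three times, with sum of squares 0.0469. Then λ = 66 × 0.0469 / 0.5 = 6.19, and F(3, 192) gives 0.52. The equivalent interaction f is √(0.0469/4) = 0.11, below both .25 and .15.

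**The case against.** Several replies carry weight.

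- *The arithmetic is right.* The stated inputs do return about 0.72. V.N.5 gives f=.25 first and converts it to kilograms separately. If f refers to the four-visit mean, the power stands and only the kilogram translation is off. That baseline was treated as a visit that differs is inferred from the visit list and the match at m=4; the plan does not say so. This stands, but then the 2.5 kg is wrong, because about 3.3 kg would be needed after baseline. Either way the power and the kilogram difference do not belong together.
- *Sixty-six is conservative.* The mixed model uses incomplete cases. A reader might infer that the planned test can have at most 0.47 power. The documents do not support that: 0.47 belongs to 66 completers, r=.50 and no more than 2.5 kg at any visit. Partial data raise it, although even 120 completers reach only 0.73.
- *The main effect is not the deciding test.* V.N.5 calls the trajectory comparison the main outcome, and the plan also describes growth curves and contrasts at each time point. A reader might infer that the whole trial would probably miss a 5.5 lb effect; that does not follow from this one figure. The 0.99 does not settle the matter either, since it takes f=.25 as an interaction effect.
- *The outcome may be weight change,* because the 5 kg is an SD of weight loss. Then only three visits are informative. The unadjusted change score at r=.50 has λ = 16.5 × 0.25 / 0.667 = 6.19 and power 0.69. The plan does not state that model.

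Two further readings go too far. Baseline adjustment does not restore 0.72 whatever the time course: with a linear rise it gives 0.40. Very low power computed on raw body weights would need a between-patient SD of weight that no section gives, so it is not relied on here.

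**Conclusion.** The .7199 and the 2.5 kg are inconsistent with the planned visits. On the plan's own basis (66 completers, r=.50, 2.5 kg at weeks 8, 26 and 52, 1:1 allocation, equal correlations) the four-visit main effect has power of about 0.47. It is lower if the effect takes time to build. In the flat case it is higher with partial data: about 0.52 to 0.68 if 27 to 54 dropouts supply baseline and week 8. Only a post-baseline difference of about 3.3 kg would justify 0.72 with 66 completers.

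This should be fixed, but it is not decisive for the trial, because the plan rests its main claim on trajectories. That claim has the same difficulty: the 3-df interaction has about 0.52 power for a flat 2.5 kg difference at N=66, not 0.99.

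**What to change.** 1. In Statistical Plans, replace the four-visit group main effect with a treatment comparison on the post-baseline visits. Either enter the baseline value of the outcome as a covariate, or keep baseline in the mixed model with its mean constrained equal across arms.
2. In V.N.5, say whether f=.25 is the average over four visits or the post-baseline difference, and make the kilogram figure agree.
3. Restate the power with its conditions (66 completers, 2.5 kg by the last visit, r=.50): about 0.47 for the main effect as now written with a flat effect; for the baseline-adjusted post-baseline mean, 0.87 (flat), 0.73 (half at week 8) or 0.40 (linear rise). Any gain claimed from partial data should come with the assumed dropout pattern.
4. Recompute the 0.99 and 0.83 for the trajectory test that will be used, from the same visit-by-visit differences in kilograms.

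The cost is analysis wording, one degree of freedom if baseline is a covariate, and one recomputed paragraph. Baseline is already collected; no patients, visits or data are added.

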2. Weight Loss Measures: Weight loss measures including measurement of weight, body mass index (BMI), waist circumference, and body composition (% body fat) will occur at each visit of the study. Weight will be obtained on the same clinic scale for all patients. All weight measurements will occur at the same time of day for each appointment. Height measurement will be made at the first screening appointment to calculate BMI. The measurement of the 'waist' is taken at the point midway between the iliac crests and the costal margins. Measurement of the waist is thought to reliably relate to cardiovascular risk, as it reflects visceral adiposity (66) and can assist in diagnosis of the metabolic syndrome. A waist measurement of 35 inches or greater is part of the diagnostic criteria for the metabolic syndrome diagnosis for women and greater than 40 inches meets diagnostic criteria for men. Percent body fat analysis will be performed using a small machine that patients hold in their hands for one minute. This machine emits an electromagnetic signal that uses the differential impedance of bodily tissues to calculate percent body fat. Patients using pacemakers cannot use this device because of concerns of possible interference.

3. Laboratory Measures: Laboratory measures that include hemoglobin A1c, fasting blood glucose, cholesterol, triglycerides, c-reactive protein, and insulin to determine insulin resistance as calculated by the HOMA method. Urine will be collected and tested for diabetes. Laboratory tests will be completed at 3-month intervals.

4. Psychiatric Assessments: These measurements are being done to assess the impact of the behavioral program on overall psychiatric condition as well as the psychiatric factors that impact weight loss. Formal psychiatric assessments will be done at baseline at the end of the 8 weeks of classes, 6 months, 12 months, and end of study. Quality of life will be assessed at baseline and end of the study.

a) Brief Psychiatric Rating Scale (BPRS): The BPRS is a 24 item scale that assesses many aspects of psychopathology including positive psychotic symptoms, (hallucinations, paranoia, unusual thought content and conceptual disorganization) as well as symptoms of anxiety and depression (67). The BPRS will be used to screen positive, negative, and cognitive symptoms that might impact patients' ability to lose weight (15 minutes).

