3. Repeated measures analyses: We propose to longitudinal (repeated measures) analyses to maximize the additional power we gain by observing the same subjects across 12 months.. Repeated measures analyses permit contrasts at each time point, and also describe and compare trajectories of change (trends), speed and durability of effects. We will also conduct separate cross-sectional to provide outcome data for ongoing safety review, interim progress reports, study oversight and conduct.

The primary design for longitudinal (repeated measures) analyses of continuous outcome scales will be a 2-group (treatment) mixed general linear model of timepoints nested within participants. This is very general linear model that permits flexibility in specifying the nature of the covariances among the dependent measures, allows time-dependent, within and between subject covariates, and permits incomplete (i.e., missing) data. Analyses of trends across the monthly assessments will be done using growth curve model within the mixed model analysis of covariance design with repeated measures described above. We propose to model a linear trend of time unless inspection clearly suggests nonlinearity. By fitting a slope over time (and intercept) for each participant who has baseline and at least one other measure, this method makes good use of all the data, and is robust even if some of the some measures are missing. The use of the mixed general linear model for all cross-sectional and linear hypotheses ensures that results will be comparable across different analyses and provide a framework to include group, person and time-specific covariates if it becomes necessary. The preliminary analyses have shown that this analysis strategy provides meaningful results even with partial data and suggests that we will exceed the originally projected power.**4. Stratification:** Randomization will be stratified by type of antipsychotic and presence of mood stabilizer medication (e.g., depakote, lithium) to assure balance on olanzapine and clozapine by randomizing within three strata – olanzapine, clozapine, and all other antipsychotics -- using three separate randomization lists. Because such stratification can adversely affect statistical power by creating artificially comparable (and heterogeneous) groups, two dummy variables coding olanzapine and clozapine at baseline will be included in all analyses as covariates.

4. Statistical Plans:

Primary Hypotheses:

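### The trajectory powers of 0.99 and 0.83 are not powers for the 5.5 lb difference that the power section equates with f=0.25; on that section's own basis, 3-df power for 5.5 lb is at most 0.66

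*Combined protocol and SAP*

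**What the plan says.** Section V.N, item 5 (Power Analysis) sets f=0.25 for all calculations, with two-sided alpha 0.05. It takes an SD of weight loss of about 5 kg and concludes: "A medium effect would thus translate into a group difference of about 2.5 kg or about 5.5 pounds". No other f is converted to weight.

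The sample basis is 120 enrolled with 45% attrition, so that "at least 66 subjects will provide complete the study and provide 4 data points". Three powers follow:

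- 0.7199 for the main difference between groups, at a within-subject correlation of 0.50;
- 0.99 for the difference in trajectories, in the words "our main outcome variable is 0.99, and even if the effect is as small as" f=0.15;
- 0.83 for trajectories at that f=0.15.

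The section calls the completer basis conservative because, of incomplete cases, "they still provide some information and will increase power".

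The documents do not settle which visits the weight test uses:

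- Section V.N, item 4 (Statistical Plans) says to "use analysis of repeated measures using the assessments at baseline, 8 weeks, 6 months, and 12 months".
- Section V.N, item 3 says "Analyses of trends across the monthly assessments will be done using growth curve model", and "We propose to model a linear trend of time unless inspection clearly suggests nonlinearity".
- Section V.G.2 says that weight, BMI, waist and "body composition (% body fat) will occur at each visit of the study". The Schedule of Events lists 19 such visits (0 to 18).

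**The concern.** Since f=0.25 is said to underlie everything and 5.5 lb is its only stated meaning, a reader will take 0.99 as the power of the main test to detect 5.5 lb, and 0.83 as the power for something smaller still. But f means different things in the two tests. For the main effect it is half the standardized mean difference. For a group-by-time interaction it measures how much the group difference varies across visits.

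Sections I.A and IV.E.2 use 5.5 lb as the benchmark predicted in the original proposal. If the trial gave a null or modest result, a reader relying on 0.99 could wrongly conclude that 5.5 lb had been all but ruled out.

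**Working it through.** **Inputs.** From the power section: N=66, 4 data points, r=0.50, alpha 0.05 two-sided, SD of weight loss 5 kg, difference 2.5 kg. Assumed: 1:1 allocation, and compound symmetry, which a single r implies. At r=0.50 the SD of change, σ√(2(1−r)), equals the SD at a visit, so 2.5 kg is 0.5 SD on either scale.

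**Step 1: reproduce the plan's figures** (noncentral F).

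- Main effect: λ = f²·N·4/(1+3r) = 0.0625·66·4/2.5 = 6.6; df 1, 64; power 0.716 (stated 0.7199).
- Interaction, f=0.25: λ = f²·N·4/(1−r) = 0.0625·66·4/0.5 = 33.0; df 3, 192; power 0.999 (stated 0.99).
- Interaction, f=0.15: λ = 0.0225·66·4/0.5 = 11.88; power 0.828 (stated 0.83).

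Other forms were tried (a 1-df interaction; λ without the 1/(1−r) factor; λ without the number of visits; the partial-eta-squared form). None gives 0.83 at f=0.15. The stated trajectory powers are therefore 3-df interaction powers.

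**Step 2: convert 5.5 lb to an interaction f.** Let d_t be the group gap at visit t in SD units. Then f = ½·SD_t(d_t), and λ = (N/4)·Σ(d_t − d̄)²/(1−r) = 33·Σ(d_t − d̄)². Randomization makes the expected gap zero at baseline. With every later gap between 0 and 0.5:

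- The largest sum of squares is 0.25, with two visits at 0 and two at 0.5. So f ≤ ½·0.25 = 0.125.
- The smallest, if the gap does reach 0.5, is 0.125, at (0, 0.25, 0.25, 0.5). So f = 0.088.

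**Step 3: power for 5.5 lb, 3-df test, df 3 and 192.**

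| Shape of gap (baseline, week 8, months 6 and 12) | λ | Power |
|---|---|---|
| 0, half, half, full | 4.13 | 0.36 |
| Linear over visits | 4.58 | 0.40 |
| Linear over months | 4.81 | 0.42 |
| Full from week 8 | 6.19 | 0.52 |
| Full from month 6 | 8.25 | 0.66 |

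A grid over all shapes confirms 0.36 and 0.66 as the extremes.

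**Step 4: the single-df slope on the same four visits.** Centring months 0, 2, 6 and 12 gives −5, −3, 1, 7, with sum of squares 84, so λ = 33·(Σ c_t d_t)²/84. The linear gap gives 4.81 (power 0.59), the week-8 step 2.46 (0.34) and the 6-month step 6.29 (0.70).

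**Step 5: the gaps that 0.99 and 0.83 imply.** The gap scales with f. For f=0.25 the minimum is 2.5·0.25/0.125 = 5.0 kg (11.0 lb), rising to 2.5·0.25/0.0884 = 7.1 kg (15.6 lb). For f=0.15 it is 3.0 to 4.2 kg (6.6 to 9.4 lb).

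**Step 6: using all 19 weight visits.** This needs a between-patient slope variance that the documents do not give. As an assumption range, hold the variance of 12-month change at 25 kg² and let slope variance be 0%, 25%, 50% or 100% of it. For 66 completers, a slope test with linear divergence to 2.5 kg then has power 0.98, 0.86, 0.72 or 0.52. For a step at week 8 the range is 0.65 to over 0.99.

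**Step 7: the preliminary effect.** At 11.8 lb (5.35 kg), the least favourable shape still gives four-visit 3-df power of 0.96.

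**The case against.** The strongest reply is that the section makes no arithmetic error and never states outright that 0.99 is the power for 5.5 lb. That is true, but it offers no other meaning for f=0.25 and says nothing to limit the conversion to the main effect.

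The 0.66 ceiling also depends on the model:

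- **Correlation structure.** AR(1) with the SD of change held at 5 kg gives 0.67 at best at the stated r=0.50. It reaches 0.80 only at r=0.9, which the plan does not state; a linear gap stays at about 0.36.
- **Baseline as a constrained covariate.** This raises the best case to about 0.75, and the linear case to 0.53.
- **Meaning of the SD.** Reading 5 kg as the SD of weight itself, with a correlation well above 0.50, would raise power (best case 0.88 at r=0.7, more at higher r). The plan calls it the SD of weight loss and states 0.50.
- **2.5 kg as an average over the four visits.** Power would then be about 0.80 (from week 8), 0.96 (linear over visits) or over 0.99 (from month 6). But the largest gap would be 3.3 to 5.0 kg, which does not fit Sections I.A and IV.E.2, where 5.5 lb is compared with a one-year difference.

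The completer basis is conservative, as the plan says. Yet even 120 complete cases would give only 0.91 at best, and 0.67 for a gap linear over visits. The 19-visit analysis could come close to 0.99, but only under a slope variance the plan does not state. What stands is that the shortfall is shown for the four-visit completer basis on which the section computes its powers, not for every analysis the plan might permit. The 5 kg SD comes from an outside study, and the pound figures in Step 5 scale with it.

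**Conclusion.** The concern holds. The stated powers are correct for an interaction f of 0.25 and 0.15, but neither is the power for 5.5 lb. A largest gap of 5.5 lb yields at most half the interaction f that the section assigns to it (0.125 against 0.25). On 66 completers, four visits, compound symmetry and a 5 kg SD of change, 3-df power is 0.36 to 0.66 rather than 0.99; the four-visit slope test gives 0.34 to 0.70 for the shapes tried.

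The planned sensitivity to 5.5 lb is therefore overstated on the section's own basis. This does not show that the trial is too small: power at the preliminary 11.8 lb is at least 0.96 for any shape of gap. It should be fixed because it misstates what the main test can detect.

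**What to change.** Keep N=120 and reword the power paragraph:

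1. Restrict the 2.5 kg (5.5 lb) translation to the between-group main effect, and state that 0.7199 assumes the full difference at all four visits, baseline included.
2. State the test, visits and trajectory to which 0.99 and 0.83 belong, with the largest gap each implies (at least about 11 lb and 6.6 lb).
3. As the power for 5.5 lb, replace them with the power of the planned group-by-time test for a stated trajectory starting from zero difference. Alternatively, give the difference detectable at 80% power: on 3 df, four visits and 66 completers, about 3.4 kg (7.4 lb) if sustained from week 8, or 3.8 to 3.9 kg (8.4 to 8.6 lb) if linear. Label these as illustrative completer figures that partial cases and further weight visits would improve.
4. Say which visits the weight test uses. If it uses all the monthly visits, state the slope variance assumed.

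The cost is one rewritten paragraph and a less favourable stated power for 5.5 lb. Sample size, analysis and conduct do not change.
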